3.6 STUDY CALENDAR

Cycle	Screening	1				2				3	4	Daily	Every Cycle	Every 3 cycles (Cycle 4 onwards)	Disease Progression/ Withdrawal from study
		1	8	15	22	1	8	15	22	1	1				
Day (D) of Cycle (+/- 3 days)		1	8	15	22	1	8	15	22	1	1				
Weeks		1	2	3	4	5	6	7	8	9	13				
Visit	1	2		3		4				5	6				
Informed consent	X														
Medical history	X														
Eligibility Evaluation	X														
History & Physical examination	X ^a	X		X		X				X	X		X		X
ECHO	X														
Vital signs/ weight	X ^a	X		X		X				X	X		X		X
BP Monitoring												X			
12-lead ECG	X ^b	X ^c	X ^d		X ^d		X								
(Chem 20)/ (CBC)	X ^a	X				X				X	X		X		X
Chem 20			X	X	X		X	X	X						
Thyroid and parathyroid function tests	X													X	
Urinalysis	X ^a					X				X	X		X		
Pregnancy test	X ^a												X		
ECOG performance status	X ^a					X				X	X		X		X
RECIST Assessment	X ^b										X			X	
Dispense ZD6474		X				X				X	X		X		
Sample for Biomarkers	X ^b			X		X				X	X		X		X
Tolerability/ AE reporting		X		X		X				X	X		X		X
Concurrent treatment	X ^b	X		X		X				X	X		X		X

^a Should be performed within 7 days prior to enrolment on study, pregnancy test performed only in women of childbearing potential

^b Should be performed within 4 weeks prior to enrolment on study

^c A 12-lead ECG should be obtained on day 1, cycle 1 before the first dose of ZD6474 and repeated 4-8 hours after the first dose

^d Should be performed 4-8 hours after ZD6474 dose

3.7 CONCURRENT THERAPIES

Coadministration of ZD6474 and drugs with potent CYP3A4 inducer effects are not allowed. Agents with potent inhibitory effects on CYP3A4 should be avoided where possible. (Please see [Appendix D](#)) Other agents with some modulation of and/or metabolism through CYP3A4 can be used with caution at the discretion of the Principal Investigator ZD6474 should also not be administered in patients receiving drugs known to prolong QT interval or induce torsades de point. (Please see [Appendix C](#)). No concurrent systemic anti-neoplastic therapy for VHL-associated tumors will be allowed.

3.8 SURGICAL GUIDELINES

Major elective surgical procedures should not be scheduled during protocol treatment or within 4 weeks of the last dose of drug. Patients undergoing unexpected major surgical procedures should have ZD6474 withheld. Treatment may be resumed at a later date at the discretion of the PI, no earlier than 4 weeks post-operatively, with adequately healed incisions.

3.9 OFF STUDY CRITERIA/OFF TREATMENT CRITERIA

In the absence of treatment delays due to adverse event(s), treatment may continue until one of the following criteria applies:

- Disease progression per RECIST criteria of targeted renal lesions
- Disease progression of non-renal lesions requiring surgical intervention or systemic anti-neoplastic therapy. Vandetanib may be restarted in patients undergoing resection of non-renal VHL lesions once the surgical incisions have adequately healed, if in the opinion of the PI, this is likely to offer clinical benefit (e.g. patients demonstrating an ongoing response in their renal tumors while on vandetanib).
- Intercurrent illness that prevents further administration of treatment,
- Unacceptable adverse event(s) that necessitates discontinuation of ZD6474, including most grade 4 and recurrent grade 3 toxicities (CTCAE v3) as outlined in section 3.3 as well as any other adverse event that renders further treatment unsafe in the opinion of the investigator
- Patient decides to withdraw from the study, or
- General or specific changes in the patient's condition render the patient unacceptable for further treatment in the judgment of the investigator.

In the event of a complete radiologic response, treatment will continue for 2 cycles beyond CR. Patients may be retreated at the discretion of the PI in the event of disease recurrence.

3.10 POST-TREATMENT FOLLOW-UP

Patients with unresolved toxicities (to \leq CTCAE 3.0 grade 1) may be followed to enable monitoring and/or management of these toxicities. Patients may be followed-up by telephone or other means of communication periodically to determine disease status.

4 SUPPORTIVE CARE

Supportive care will be provided in accordance with good medical practice

5 DATA COLLECTION AND EVALUATION

5.1 DATA COLLECTION

Data will be prospectively collected and entered in a designated database (C3D). All radiographic images will be stored in the Dept. of Radiology, Clinical Center, NIH and will be reviewed by a medically responsible investigator and/or a clinical center radiologist.

For the purposes of this study, patients should be reevaluated for response every 12 weeks. In addition to a baseline scan, confirmatory scans should also be obtained 4 weeks following initial documentation of objective response.

The PI will be responsible for overseeing entry of data into an in-house password protected electronic system and ensuring data accuracy, consistency and timeliness. The principal investigator, associate investigators/research nurses and/or a contracted data manager will assist with the data management efforts. All data obtained during the conduct of the protocol will be kept in secure network drives or in approved alternative sites that comply with NIH security standards. Primary and final analyzed data will have identifiers so that research data can be attributed to an individual human subject participant.

End of study procedures: Data will be stored according to HHS, FDA regulations and NIH Intramural Records Retention Schedule as applicable.

Loss or destruction of data: Should we become aware that a major breach in our plan to protect subject confidentiality and trial data has occurred, the IRB will be notified.

5.2 RESPONSE EVALUATION

5.2.1 Definitions

Response and progression of renal tumors will be evaluated in this study using the new international criteria proposed by the Response Evaluation Criteria in Solid Tumors (RECIST) Committee [*JNCI* 92(3):205-216, 2000]. Changes in only the largest diameter (unidimensional measurement) of the tumor lesions are used in the RECIST criteria. Note: Lesions are either measurable or non-measurable using the criteria provided below. The term “evaluable” in reference to measurability will not be used because it does not provide additional meaning or accuracy.

5.2.1.1 Measurable disease

Measurable lesions are defined as those that can be accurately measured in at least one dimension (longest diameter to be recorded) as ≥ 20 mm with conventional techniques (CT, MRI, x-ray) or as ≥ 10 mm with spiral CT scan. All tumor measurements must be recorded in millimeters (or decimal fractions of centimeters).

5.2.1.2 Non-measurable disease

All other lesions (or sites of disease), including small lesions (longest diameter < 20 mm with conventional techniques or < 10 mm using spiral CT scan), are considered non-measurable disease. Bone lesions, leptomeningeal disease, ascites, pleural/pericardial effusions, lymphangitis cutis/pulmonis, inflammatory breast disease, abdominal masses (not followed by CT or MRI), and cystic lesions are all non-measurable.

5.2.1.3 Target lesions

All measurable RCC lesions up to a maximum of five lesions per kidney and a total of ten lesions should be identified as **target lesions** and recorded and measured at baseline. Target lesions should be selected on the basis of their size (lesions with the longest diameter) and their suitability for accurate repeated measurements (either by imaging techniques or clinically). A sum of the longest diameter (LD) for all target lesions will be calculated and reported as the baseline sum LD. The baseline sum LD will be used as reference by which to characterize the objective tumor response.

5.2.1.4 Non-target lesions

All other lesions (or sites of disease) should be identified as **non-target lesions** and should also be recorded at baseline. Non-target lesions include measurable lesions that exceed the maximum numbers per organ or total of all involved organs as well as non-measurable lesions. Measurements of these lesions are not required, but the presence or absence of each should be noted throughout follow-up. If the lesions are too numerous to list, not all lesions may be listed at the discretion of the investigator and/or radiologist.

5.2.2 Guidelines for Evaluation of Measurable Disease

All measurements should be taken and recorded in metric notation using a ruler or calipers. All baseline evaluations should be performed as closely as possible to the beginning of treatment and never more than 4 weeks before the beginning of the treatment. For each restaging study, lesions will be recorded in the same order as with the baseline study.

Note: Tumor lesions that are situated in a previously irradiated area might or might not be considered measurable.

The same method of assessment and the same technique should be used to characterize each identified and reported lesion at baseline and during follow-up. Imaging-based evaluation is preferred to evaluation by clinical examination when both methods have been used to assess the antitumor effect of a treatment.

Clinical lesions. Clinical lesions will only be considered measurable when they are superficial (e.g., skin nodules and palpable lymph nodes). In the case of skin lesions, documentation by color photography, including a ruler to estimate the size of the lesion, is recommended.

Chest x-ray. Lesions on chest x-ray are acceptable as measurable lesions when they are clearly defined and surrounded by aerated lung. However, CT is preferable.

Conventional CT and MRI. These techniques should be performed with cuts of 10 mm or less in slice thickness contiguously. Spiral CT should be performed using a 5 mm contiguous reconstruction algorithm. This applies to tumors of the chest, abdomen, and pelvis. Head and neck tumors and those of extremities usually require specific protocols.

Ultrasound (US). When the primary endpoint of the study is objective response evaluation, US should not be used to measure tumor lesions. It is, however, a possible alternative to clinical

measurements of superficial palpable lymph nodes, subcutaneous lesions, and thyroid nodules. US might also be useful to confirm the complete disappearance of superficial lesions usually assessed by clinical examination.

Endoscopy, Laparoscopy. The utilization of these techniques for objective tumor evaluation has not yet been fully and widely validated. Their uses in this specific context require sophisticated equipment and a high level of expertise that may only be available in some centers. Therefore, the utilization of such techniques for objective tumor response should be restricted to validation purposes in reference centers. However, such techniques may be useful to confirm complete pathological response when biopsies are obtained.

Tumor markers. Tumor markers alone cannot be used to assess response. If markers are initially above the upper normal limit, they must normalize for a patient to be considered in complete clinical response. Specific additional criteria for standardized usage of prostate-specific antigen (PSA) and CA-125 response in support of clinical trials are being developed.

Cytology, Histology. These techniques can be used to differentiate between partial responses (PR) and complete responses (CR) in rare cases (e.g., residual lesions in tumor types, such as germ cell tumors, where known residual benign tumors can remain).

5.2.3 Response Criteria

5.2.3.1 Evaluation of target lesions

Complete Response (CR):	Disappearance of all target lesions
Partial Response (PR):	At least a 30% decrease in the sum of the longest diameter (LD) of target lesions, taking as reference the baseline sum LD
Progressive Disease (PD):	At least a 20% increase in the sum of the LD of target lesions, taking as reference the smallest sum LD recorded since the treatment started or the appearance of one or more new lesions
Stable Disease (SD):	Neither sufficient shrinkage to qualify for PR nor sufficient increase to qualify for PD, taking as reference the smallest sum LD since the treatment started

5.2.3.2 Evaluation of non-target lesions

Complete Response (CR):	Disappearance of all non-target lesions and normalization of tumor marker level
Incomplete Response/ Stable Disease (SD):	Persistence of one or more non-target lesion(s) and/or maintenance of tumor marker level above

the normal limits

Progressive Disease (PD): Appearance of one or more new lesions and/or unequivocal progression of existing non-target lesions

Although a clear progression of “non-target” lesions only is exceptional, in such circumstances the opinion of the treating physician should prevail, and the progression status should be confirmed at a later time by the review panel (or study chair).

Note: If tumor markers are initially above the upper normal limit, they must normalize for a patient to be considered in complete clinical response.

5.2.3.3 Evaluation of best overall response

The best overall response is the best response recorded from the start of the treatment until disease progression/recurrence (taking as reference for progressive disease the smallest measurements recorded since the treatment started). The patient's best response assignment will depend on the achievement of both measurement and confirmation criteria.

Target Lesions	Non-Target Lesions	New Lesions	Overall Response
CR	CR	No	CR
CR	Incomplete response/SD	No	PR
PR	Non-PD	No	PR
SD	Non-PD	No	SD
PD	Any	Yes or No	PD
Any	PD	Yes or No	PD
Any	Any	Yes	PD

Note:

- Patients with a global deterioration of health status requiring discontinuation of treatment without objective evidence of disease progression at that time should be classified as having “symptomatic deterioration.” Every effort should be made to document the objective progression, even after discontinuation of treatment.
- In some circumstances, it may be difficult to distinguish residual disease from normal tissue. When the evaluation of complete response depends on this determination, it is recommended that the residual lesion be investigated (fine needle aspirate/biopsy) before confirming the complete response status.

5.2.4 Confirmatory Measurement/Duration of Response

5.2.4.1 Confirmation

To be assigned a status of PR or CR, changes in tumor measurements must be confirmed by repeat assessments that should be performed ≥ 4 weeks after the criteria for response are first met. In the case of SD, follow-up measurements must have met the SD criteria at least once after study entry at a minimum interval of 8 weeks

5.2.4.2 Duration of overall response

The duration of overall response is measured from the time measurement criteria are met for CR or PR (whichever is first recorded) until the first date that recurrent or progressive disease is objectively documented (taking as reference for progressive disease the smallest measurements recorded since the treatment started).

The duration of overall CR is measured **from** the time measurement criteria are first met for CR until the first date that recurrent disease is objectively documented.

5.2.4.3 Duration of Stable Disease

Stable disease is measured from the start of the treatment until the criteria for progression are met, taking as reference the smallest measurements recorded since the treatment started.

5.2.5 Evaluation of non-renal tumors associated with VHL

Evaluation of the effect of ZD6474 on non-renal tumors associated with VHL disease is one of the secondary end-points of this study. Since there is significant interpatient variability in the location and number of visceral and non-visceral tumors, each tumor type will be assessed individually. In each individual patient, the presence of one or more of the following tumors at baseline will be documented and response following treatment with ZD6474 will be assessed:

- 1) Pancreatic tumors/cysts
- 2) CNS Hemangioblastomas
- 3) Pheochromocytomas

5.2.5.1 Identification and measurement of lesions to be followed, and response criteria will follow the scheme outlined in Sections [5.2.1](#) to [5.2.4](#)

5.2.5.2 Evaluation of retinal angiomas will include the following:

- a) Measurement of visual acuity
- b) Size-Largest unidimensional measurements will be recorded where appropriate
- c) Visual field evaluation
- d) Fluorescein leakage

Since standard tumor response criteria such as RECIST cannot be applied to ocular lesions, changes in the above parameters will be recorded descriptively.

5.2.5.3 Patients with progressive disease in non-renal lesions which require medical or surgical intervention shall be taken off study for progressive disease. Patients with progressive disease in non-renal lesions not requiring intervention but stable disease or responding disease in renal lesions will be continued on ZD6474 to the discretion of the PI or Study Chair.

5.3 TOXICITY CRITERIA

CTCAE term (AE description) and grade: The descriptions and grading scales found in the revised NCI Common Terminology Criteria for Adverse Events (CTCAE) version 4.0 will be utilized for AE reporting. All appropriate treatment areas should have access to a copy of the CTCAE version 4.0. A copy of the CTCAE version 4.0 can be downloaded from the CTEP web site (<http://ctep.cancer.gov>)

6 STATISTICAL SECTION

This is a phase II study to establish whether treatment of ZD6474 in patients with von Hippel Lindau disease and renal tumors results in an adequate fraction of clinical responses (partial response plus complete response) to warrant further development. The study will be conducted with a Simon two-stage optimal design (Simon R. Controlled Clinical Trials 10:1-10;1989) which allows for an early look for futility. For the purposes of phase II evaluation, clinical response will be defined as either a partial or complete response occurring at any time after initiation of therapy. All responses must be confirmed ≥ 4 weeks after the initial response is documented. Twelve patients will be accrued into the first stage. If 1 or more of the 12 patients respond, accrual will proceed to the second stage of the design. Twenty-five additional patients will be accrued in the second stage for a total accrual of 37 patients. If 4 or more of 37 respond, ZD6474 will be considered worthy of further investigation in this population. If fewer than 4 patients of 37 respond, the agent will be considered to have insufficient activity for further investigation. If after the first 12 patients have been accrued to the study, no patient has had a confirmed response, further accrual will be temporarily suspended for up to a year or until at least one response is seen; if no responses are seen within one year of accrual of the twelfth patient, no further patients will be accrued and the study will not proceed to the second stage.

6.1 TWO-STAGE DESIGN

The optimal two-stage design is based on the following design parameters. The fraction of clinical responses is 5% if the agent is ineffective ($P_0=0.05$), while a fraction of clinical responses of 20% ($P_1=0.2$) will be considered worthy of further testing. The probability of falsely concluding that the agent is effective when it is truly ineffective is 0.1 (alpha) and the probability of falsely concluding that the agent is ineffective when it is truly effective is 0.1 (beta). Under this design, the probability of stopping accrual early if the proportion of responses is 5% is 54%.

6.2 RESPONSE FREQUENCY

The response frequency for non-renal tumors associated with VHL will be estimated as a secondary objective. Other secondary objectives (Section 1.1) include examining the effect of ZD6474 on, (i) plasma biomarkers of angiogenesis such as VEGF, (ii) endothelial progenitor cells and circulating endothelial cells, (iii) time to progression (defined as the time from the start

of treatment to progression as defined by RECIST criteria, with death being treated as a censored event), and (iv) progression free survival (defined as time from initiation of treatment to either progression as defined by RECIST criteria, section 5.2.3.3, or death). The follow-up times for biomarker endpoints are given in Sections 3.4 and 3.5. Analyses will focus on comparing changes in these biomarkers on treatment from the pre-study measurement. Longitudinal changes in continuous biomarkers (eg. plasma VEGF) or imaging outcomes will be analyzed using paired Wilcoxon-ranked sum tests (which compares measurements at a single post-treatment time point with measurements at the pre-treatment time point) as well as with linear mixed models (which incorporates all follow-up times when evaluating change). Evaluation of time to progression and progression free survival will be based on restaging studies performed approximately every 12 weeks and will be summarized using Kaplan-Meier curves. Available pre-treatment data on tumor size and growth rates will be used to determine if parameters such as TTP/stability are affected by treatment both within individual patients and in the entire treatment group.

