1 INTRODUCTION

1.1 STUDY OBJECTIVES

1.1.1 Primary Objective

- To assess the overall response rate in VHL patients with renal tumors treated with single agent ZD6474

1.1.2 Secondary Objectives:

- To study the safety and tolerability of ZD6474
- To evaluate time to progression and progression-free survival in VHL patients receiving ZD6474
- To study the effect of ZD6474 treatment on non-renal tumors associated with von Hippel Lindau disease (pancreatic tumors, pheochromocytoma, CNS hemangioblastomas)
- To investigate the effect of ZD6474 on circulating endothelial cells and endothelial progenitor cells and to explore the utility of these markers as surrogates of angiogenesis inhibition
- To investigate the effect of ZD6474 on biomarkers of angiogenesis such as plasma VEGF and soluble VEGFR2

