Several phase I trials have been conducted in human subjects. Trial 6474IL/0001 (Western study) was conducted as a multicenter, dose escalation phase I trial evaluating 50, 100, 200, 300, 500 and 600mg doses administered orally as a daily single dose. A total of 77 patients have been treated on this trial at various dose levels, including an expanded cohort of 19 and 25 patients respectively at the 100mg and 300mg dose levels who were enrolled to better evaluate the effect of ZD6474 on QT interval and ST, T wave changes. A second phase I trial conducted in Japan (TVE-15-11) followed a dose escalation pattern evaluating 100, 200, 300 and 400mg daily oral doses. A total of 18 patients have been accrued on this trial.

Pharmacokinetics

Pharmacokinetic data obtained from the Western and Japanese studies were comparable. Absorption was highly variable, with individual patients having a T_{max} as late as 24 hours post-dose. Following achievement of maximum plasma concentration, C_{max} declined in a biphasic manner. Terminal half-life was estimated to be about 4-5 days and appeared to be independent of dose. Both mean AUC and C_{max} increased with increasing dose in a linear manner with about 2 to 6 fold in inter-individual variability in AUC for a given dose. A comparison of the mean weekly trough levels suggest that steady state was achieved by day 29, with marked accumulation between day 1 and 29.

Adverse Events

The most common adverse events seen on both trials were:

- 1) Rash- At least 2 distinct types of rash were seen- A macular erythema and a follicular (acneiform) rash. Rash was reported in 54 (72%) patients in the Western and 14 (77.8%) patients in the Japanese study. The occurrence of rash appeared to be dose-dependent.

- 2) Gastrointestinal toxicity- Diarrhea was reported in 42 (56%) of the Western patients and 10 (56%) of the Japanese patients. Other common GI side effects seen the western and Japanese studies included nausea (39% in the Western and 22% in the Japanese studies), vomiting (22% and 17% respectively), anorexia (29% and 28% respectively) and constipation (24% in the Western study).
- 3) Central Nervous System- Headaches were reported by 19 (25%) patients and dizziness by 14 (17%) patients in the Western study. 27% of the patients in the Japanese study reported headaches.
- 4) Cardiovascular toxicity-
 - a. In the western trial, 6 patients (8%) had T-wave or ST-segment changes consistent with repolarization abnormalities.

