3.4 RESEARCH STUDIES

Sample acquisition and planned studies

Blood samples for evaluation of basal plasma levels of angiogenesis biomarkers such as VEGF and to assess the effect of ZD6474 on these biomarkers will be obtained on study entry and at each clinic visit. 5-10 cc of venous blood will be collected into lavender top EDTA tubes and thoroughly mixed.

Peripheral blood (four CPT tubes containing sodium citrate) will be obtained pre-treatment and post-treatment with ZD6474 and coded samples will be used for analysis of angiogenesis markers such as circulating endothelial cells (CEC) and circulating endothelial progenitor cells (CEP). The time points may vary as the optimal time vis a vis treatment needs to be empirically determined. Four CPT tubes containing sodium citrate (blue-black speckled top tubes) of peripheral blood will be sent to [name]'s laboratory in the Medical Oncology Branch, CCR, NCI. The CEC and CEP analysis will be performed using multiparameter flow cytometry, and may include ancillary studies such as real-time RT-PCR analysis of gene expression and *in vitro* endothelial cell culture. These studies are exploratory and intended to evaluate the utility of CECs and CEPs as surrogates for inhibition of angiogenesis following administration of ZD6474.

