Although there is no universally accepted surrogate for angiogenesis inhibition, evaluation of CECs and CEPs have been proposed and validated by several groups (41-46). [name] lab has collaborated with other groups ([name], MD Anderson Cancer Center, and the Angiogenesis Core at the Beth Israel and Deaconess Medical Center) to standardize flow cytometric analyses of peripheral blood for evaluation of CEC/CEP. For this analysis, peripheral blood is drawn into 4 CPT citrate tubes. Mononuclear cells are isolated by centrifugation, washed with PBS, and FcR solution (Miltenyi) is added to block non-specific binding. Although the antibodies and fluorochromes used may vary, for identification of CECs and CEPs, cells are typically stained with FITC- conjugated anti-CD31, PerCP-conjugated anti-CD45, APC-conjugated anti-CD133, Hoechst 33258 and PE-conjugated CD146 and analysed on an LSR II flow cytometer (BD Biosciences), using LSR II-equipped digital data acquisition and FlowJo cytometric data analysis software. The CEC and CEP cell concentrations are calculated as a percentage of the total number of mononuclear cells or as the number of cells/microliter of whole blood after an evaluation of a minimum of 10^5 cellular events, and preferably 10^6 cellular events. CEC cells are defined by the co-expression, or absence of expression on a single cell of the following parameters: CD45-, CD31+, CD133- and CD146+, Hoechst 33258 (viable CEC) or CD45-, CD31+, CD133- and CD146+, Hoechst 33258+ (nonviable CEC). CEP cells are defined by the co-expression, or absence of expression on a single cell of the following parameters: CD45- or dim, CD31+, CD133+ and CD146-, Hoechst 33258- (viable CEP) or CD45- or dim, CD31+, CD133+ and CD146-, Hoechst 33258+ (nonviable CEP).

The outcome measures will be the number of CEC and CEP per 10^6 mononuclear cells or per microliter of peripheral blood, analyzed in samples taken before and after treatment. These numbers will then be examined for correlations with various parameters to assess their potential utility as surrogate biomarkers for drug activity, for establishing the optimal biologic dose, for patient stratification, and monitoring of therapy-related side effects.

In addition to multi-parameter flow CEC and CEP analysis, if there are a sufficient number of cells in the mononuclear fraction the cells will be set up *in vitro*, according to standard methods, for the endothelial progenitor cell colony forming assay (47, 48).

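### Does Section 6.2 test pre/post biomarker and imaging changes with an independent-groups Wilcoxon test that throws away the pairing?

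*Combined protocol and SAP*

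**What the plan says.** Section 6.2 first states the target of the biomarker analyses: "Analyses will focus on comparing changes in these biomarkers on treatment from the pre-study measurement". It then says that continuous biomarkers and imaging outcomes "will be analyzed using paired Wilcoxon-ranked sum tests". A parenthesis explains that the test "compares measurements at a single post-treatment time point with measurements at the pre-treatment time point". The same sentence adds a second analysis, "as well as with linear mixed models (which incorporates all follow-up times when evaluating change").

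Section 3.4 describes the circulating endothelial and progenitor cell counts (CEC/CEP) as "analyzed in samples taken before and after treatment". It says of their sampling: "The time points may vary as the optimal time vis a vis treatment needs to be empirically determined". It also calls these cell studies exploratory. Plasma markers such as VEGF have a fixed schedule in the same section: at entry and at every clinic visit.

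All of this serves secondary objectives in Section 1.1.2, for example "To investigate the effect of ZD6474 on biomarkers of angiogenesis such as plasma VEGF and soluble VEGFR2". The primary question is the response rate, decided by the two-stage rule in Section 6.

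**The concern.** There is no standard procedure called a paired rank-sum test. The rank-sum (Mann-Whitney) test treats its two samples as independent. The test for within-patient differences is the signed-rank test. A reader who goes by the test's name alone would conclude that the pre- and post-treatment values are to be compared as if they came from different patients.

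That would matter. Repeated measurements in one patient are usually positively correlated, and the independent-groups test then uses a variance that is too large. It becomes conservative and loses power, so a real effect on VEGF, soluble VEGFR2, CEC/CEP or imaging could be reported as absent.

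A second worry is that Section 6.2 does not name the single post-treatment visit, while Section 3.4 leaves some timing to be found empirically. That could allow the visit with the largest change to be picked after the data are seen.

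**Working it through.** **1. The plan's own figures.** The documents give no level, power or effect size for the Wilcoxon analysis, so there is nothing of that kind to reproduce. The figures they do give belong to the primary design in Sections 6 and 6.1: stop at 0 of 12 responders, succeed at 4 or more of 37, response rates of 5% and 20%.

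- Probability of early stopping at 5%: 0.95^12 = 0.540 (stated: 54%).
- Exact two-stage calculation: type I error 0.0935 (stated limit 0.10) and power 0.902 (stated beta 0.10).

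These reproduce, and no biomarker test enters them.

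**2. Which test does the text specify?** Four features of Section 6.2 and the design bear on this:

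| Feature | Paired test | Independent-groups test |
|---|---|---|
| The qualifier *paired* | fits | contradicts |
| Target is change from the pre-study value | fits | does not use changes |
| Comparison of one post-treatment with the pre-treatment time point | fits | possible only if patient identity is ignored |
| Single-arm study | fits | no second group exists |

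Only the words *ranked sum* point the other way. No passage calls for an unpaired comparison.

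**3. What would the misreading cost?** Let both time points have standard deviation σ and within-patient correlation ρ.

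- True variance of a within-patient difference: 2σ²(1 − ρ).
- Variance implied by independence: 2σ².
- Large-sample type I error of the unpaired test at a nominal two-sided 5%: about P(|Z| > 1.96/√(1 − ρ)).

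For ρ = 0.5 this is P(|Z| > 1.96/0.707) = P(|Z| > 2.77) ≈ 0.006. For ρ = 0.3 it is P(|Z| > 1.96/0.837) = P(|Z| > 2.34) ≈ 0.019.

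Simulation (normal data, 4,000 data sets per setting, two-sided 5%, shift 0.5 SD for power) agrees. The correlation, the shift, the 5% level and complete pairs in all n patients are assumptions; the documents give none of them.

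| n | ρ | Type I error, rank-sum | Type I error, signed-rank | Power, rank-sum | Power, signed-rank |
|---|---|---|---|---|---|
| 37 | −0.3 | 0.070 | 0.041 | 0.51 | 0.42 |
| 37 | 0 | 0.053 | 0.054 | 0.54 | 0.53 |
| 37 | 0.3 | 0.018 | 0.047 | 0.54 | 0.68 |
| 37 | 0.5 | 0.006 | 0.047 | 0.56 | 0.82 |
| 37 | 0.7 | 0.0005 | 0.043 | 0.58 | 0.96 |
| 12 | 0.5 | 0.0075 | 0.043 | 0.12 | 0.31 |

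The loss is real when ρ is positive, absent at zero and reversed when ρ is negative. In every row it arises only if the word *paired* is disregarded.

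**4. The unnamed visit.** The calendar in Section 3.6 has post-treatment biomarker samples at Cycle 1 Day 15, then on Day 1 of Cycles 2, 3 and 4, and every cycle after that. Four visits by week 13 could therefore supply the tested value. The sentence that leaves timing open stands in the CEC/CEP paragraph of Section 3.4; it does not govern plasma markers or imaging. The mixed models named beside the Wilcoxon test use every follow-up visit, so they depend neither on which visit is picked nor on the name of the rank test.

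**The case for a change.** The strongest counter-argument is about the visit, because correcting the test's name would not settle it. If an analyst tried every visit with the correct signed-rank test and reported the smallest p-value, then with no true effect and correlations of 0.3 to 0.7 the false-positive rate would be about 13 to 17% with four visits and 20 to 23% with seven, against a nominal 5%. That error would favour the drug. The arithmetic is sound, and it is true that Section 6.2 names no visit.

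It does not make the plan wrong. The plan nowhere says that the visit will be chosen by its p-value. These are secondary analyses with no alpha and no decision attached, and the CEC/CEP work is expressly exploratory. Section 3.4 makes the correlative studies conditional on samples and resources. The mixed models already give an answer that needs no choice of visit.

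Nor would one visit serve all outcomes. Cycle 2 Day 1 (week 5) looks natural, since it has a biomarker sample and Section 1.2.5 reports that "steady state was achieved by day 29". But the calendar has no RECIST assessment between screening and week 13, so imaging would have no post-treatment value at week 5. Fixing CEC/CEP at that visit would also override the protocol's stated intention to find their timing empirically.

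On the name, it is fair to say that the label contradicts itself and that signed-rank is the proper term. That part stands, as a point of terminology.

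**Conclusion.** The concern does not hold. Section 6.2 specifies a paired comparison of change from the pre-study measurement in a single-arm trial and misnames the test. Read as a whole, it leads to the signed-rank test. The power loss (0.56 against 0.82 at n = 37, shift 0.5 SD, correlation 0.5) belongs to an analysis that the plan does not request, and even there it needs positive within-patient correlation, which is plausible but not given in the documents.

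The unnamed visit is a gap in detail. Its consequences are limited by the secondary or exploratory status of the analyses and by the mixed models over all visits. This conclusion assumes that the analyst gives effect to the word *paired* and carries out the mixed models as planned. The two-stage design, its error rates and the total of 37 patients do not change.
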